2.2 Secondary Hypothesis

- 1) The extent of iron-deficient erythropoiesis, as measured by RBC zinc protoporphyrin levels, will predict the 24-hour post-transfusion RBC recovery.
- 2) There will be a good correlation ($R^2 > 0.5$) between RBC zinc protoporphyrin levels and other markers of iron status: ferritin, hepcidin, soluble transferrin receptor, reticulocyte hemoglobin.
- 3) Iron repletion will improve fatigue score³⁶ and self-reported health and wellbeing score.³⁷
- 4) Iron repletion will decrease RBC zinc protoporphyrin and soluble transferrin receptor levels.
- 5) Iron repletion will increase hepcidin, ferritin, and hemoglobin levels.
- 6) Iron repletion will improve the following neurocognitive scores:
 - a) Cognitive Function Composite Score
 - b) Executive Function
 - c) Attention
 - d) Episodic Memory
 - e) Language
 - f) Processing Speed
 - g) Working Memory
- 7) Iron repletion will improve the following emotional well-being scores:
 - a) quality of life
 - b) fatigue
 - c) depression
 - d) anxiety
- 8) Metabolite levels in the RBC unit will correlate with iron status and 24-hour post-transfusion RBC recovery.

3. Study Population

3.1 Enrollment Inclusion Criteria:

- 1) 18-75 years old;
- 2) healthy (by self report);

- 3) body weight >110 lbs;
- 4) female hematocrit >38%, male hematocrit >39%;
- 5) frequent blood donor (men ≥ 2 and female ≥ 1 RBC unit donations in past year);
- 6) ferritin <15 ng/mL;
- 7) zinc protoporphyrin >60 μ mol/mol heme.

3.2 Enrollment Exclusion Criteria:

- 1) ineligible for donation based on the New York Blood Center donor autologous questionnaire;
- 2) C-reactive protein >10 mg/L;
- 3) sickle cell trait (by self report);
- 4) systolic blood pressure >180 or <90 mm Hg, diastolic blood pressure >100 or <50 mm Hg;
- 5) heart rate <50 or >100;
- 6) temperature >99.5°F prior to donation (attempts will be made to reschedule donation if possible);
- 7) temperature >100.4°F or subjective feeling of illness prior to ^{51}Cr 24-hour RBC recovery study (to avoid the subject having a concurrent illness that may affect post-transfusion recovery); (attempts will be made to reschedule donation and ^{51}Cr 24-hour RBC recovery study);
- 8) positive results on standard blood donor infectious disease testing;
- 9) pregnancy;
- 10) taking, or planning to take, iron supplements and not willing to stop for duration of study;

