11.1 Analysis Plan

The primary null hypothesis will be tested in an intent-to-treat analysis using a t-test, or nonparametric equivalent, of the between-group difference in means of the within-subject change in the post-transfusion RBC recovery from the initial study (under iron-deficient erythropoiesis conditions) and the subsequent study performed after randomization to iron repletion or placebo. A similar approach will be used to test the secondary objectives (i.e., the between-group difference in means of the within-subject change in fatigue score,³⁶ self-reported health and wellbeing score,³⁷ zinc protoporphyrin, hepcidin, soluble transferrin receptor, serum ferritin and hemoglobin concentration).

Furthermore, because we expect variable responses to iron repletion in the experimental group, and some crossover in the placebo group, we will also perform a secondary analysis to explore the effect of iron status on post-transfusion RBC recovery. We will use multiple regression to assess whether RBC zinc protoporphyrin level increases the R^2 of a model of post-transfusion recovery predicted by treatment group membership. We will examine pre-specified demographic variables (gender [male/female], race [white/not white], age [$<50/\geq 50$ years]) to see if we can identify one or more that may be effect modifiers. These factors will be considered for inclusion in an adjusted model. The specific criteria for inclusion are: (i) difference by treatment group significant at $\alpha = 0.10$ two-sided, and (ii) related to outcome at level $\alpha = 0.10$ two-sided. If any of the pre-specified covariates meet the criteria for inclusion, they will be incorporated in an adjusted model, and that model will become the primary analysis. Otherwise, the simple model will be primary. With 60 subjects, we will have 80% power to detect a partial correlation coefficient increase of 0.33 for the unique contribution of RBC zinc protoporphyrin level.⁴⁷

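### Section 11.1 cuts age (eligible range 18 to 75) at 50 without a reason; if age has a moderate linear relation with change in recovery (partial r about 0.33, assumed), the exploratory age analyses lose about 11 to 33 points of power, while the primary treatment comparison is practically unaffected

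*Combined protocol and SAP*

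**What the plan says.** Section 11.1 (Analysis Plan) names three demographic factors, "pre-specified demographic variables (gender [male/female], race [white/not white], age [$<50/\geq 50$ years", and gives them two uses. The first is exploratory: "to see if we can identify one or more that may be effect modifiers". The second is adjustment: "These factors will be considered for inclusion in an adjusted model". A factor qualifies only if it meets both of two conditions: "difference by treatment group significant at $\alpha = 0.10$ two-sided" and "related to outcome at level $\alpha = 0.10$ two-sided". Then "If any of the pre-specified covariates meet the criteria for inclusion, they will be incorporated in an adjusted model", and that model replaces the simple one as the primary analysis.

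Section 3.1 admits donors "18-75 years old". No section explains the choice of 50, plans an analysis of age in years, or gives an expected age mix or strength of an age effect. The other predictor in the same paragraph, zinc protoporphyrin, enters the regression as a level and is not cut.

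**The concern.** Of the three factors, only age is naturally continuous. With one cut at 50, a donor of 19 is treated like one of 49, and a donor of 49 unlike one of 50. If recovery or the response to iron changes gradually with age, the two-level version discards much of that gradient.

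At stake is the trial's ability to find an age relation or an age-by-iron interaction with 60 subjects randomized, or 52 if 15% drop out. Section 11.1 says it expects variable responses to iron repletion, and age is one of only three pre-specified demographic factors that might explain them. Because a qualifying covariate changes the primary model, the effect on the treatment comparison also has to be checked.

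**Working it through.** **Inputs from the documents.** Sections 11.1 and 11.2: N = 60 (30 per arm), 26 per arm needed, SD 5.0, difference 4, two-sided alpha 0.05, selection level 0.10, partial r 0.33 (stated for zinc protoporphyrin). Section 3.1: ages 18 to 75.

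**Assumptions, because the documents are silent.** Age is linearly related to the change in recovery, with partial r of 0.33, 0.20 or 0.10. The age mix runs from uniform on 18–75 to normal with 20% aged 50 or over.

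**The plan's own figure.** The two-sample t-test with difference 4, SD 5, alpha 0.05 and power 0.80 needs 25.5 per arm, rounded up to 26. This reproduces section 11.2. The plan states no power for any age analysis.

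**Step 1: how much of age survives the cut.** The correlation between age and the two-level indicator, with p the share aged 50 or over and q = 1 − p, is √(3pq) for uniform ages and φ(z_p)/√(pq) for normal ages.
- Uniform 18–75: p = 25/57 = 0.44, correlation 0.859
- Normal, p = 0.50: 0.798
- Normal, p = 0.30: 0.759
- Normal, p = 0.20: 0.700

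The squared correlation times 60 gives the equivalent number of subjects: 60 × 0.859² = 44 down to 60 × 0.700² = 29.

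**Step 2: power for the age term.** I used a 1-df F test in a model with treatment and age, with noncentrality N·r²/(1 − r²). The cut version replaces r by r times the correlation above. At r = 0.33 and N = 60:

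| Age mix | Alpha 0.05: continuous v cut | Loss | Alpha 0.10: continuous v cut | Loss |
|---|---|---|---|---|
| Uniform | 75.9% v 61.5% | 14.4 | 84.9% v 73.2% | 11.7 |
| Normal, 50% aged ≥50 | 75.9% v 54.7% | 21.1 | 84.9% v 67.2% | 17.7 |
| Normal, 30% aged ≥50 | 75.9% v 50.4% | 25.5 | 84.9% v 63.1% | 21.7 |
| Normal, 20% aged ≥50 | 75.9% v 44.0% | 31.9 | 84.9% v 56.9% | 28.0 |

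Simulation with ages truncated to 18–75 (17% to 49% aged 50 or over) gives about 73–75% v 41–60% at 0.05 and about 83% v 54–72% at 0.10. Losses for the age-by-treatment term are similar. Formula and simulation together give the range of about 11 to 33 points. At N = 52 the formula gives 12 to 31.

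**Step 3: weaker relations, N = 60.** At r = 0.20, continuous age itself has only 34.3% power at 0.05, and the loss is about 7 to 15 points; at 0.10 it reaches about 18 if only 20% are aged 50 or over. At r = 0.10, continuous power is 11.9% at 0.05, and the loss is 2 to 5 points by formula and at most about 6 by simulation.

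**Step 4: the primary treatment comparison.** I read the first selection criterion as a difference in the covariate between arms. Under randomization that is a chance imbalance, met about 10% of the time. Treating the two criteria as roughly independent, at r = 0.33 age enters in about 0.10 × 84.9% = 8.5% of trials if continuous and 0.10 × (56.9% to 73.2%) = 5.7% to 7.3% if cut.

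When age does enter, the residual SD is 5√(1 − r²), with r attenuated as in step 1 for the cut version. Continuous age gives 4.72 and the cut gives 4.80 to 4.87. Power of the t-test at 26 per arm is 85.0% v 82.8% to 83.9%, a difference of about 1 to 2 points.

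**The case against.** Several points on the other side are sound.

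- **The effect size is borrowed.** The 0.33 is what the plan says it can detect for zinc protoporphyrin, its marker of iron-deficient erythropoiesis. It is not an expected value for age. A stable effect of age on the level of recovery also cancels in a within-subject change, so age would have to predict the change itself. This is why the loss must be stated conditionally and with the smaller values beside it.
- **The analysis is exploratory.** Age appears in no primary or secondary hypothesis and carries no power claim, so no stated figure becomes wrong.
- **A step is possible.** Section 1 describes iron deficiency as especially prevalent in women of childbearing age, which might suggest a threshold. But the plan does not link this to the cut, applies 50 to both sexes, and uses 55 as its age limit for pregnancy testing (sections 5.1 and 5.2). The documents support neither a step at 50 nor strict linearity. If the truth is a step at 50, simulated interaction power at alpha 0.05 (n = 60, ages with mean 45 and SD 14) is about 73% with the cut and 53% with a linear term. This cost is real and argues for allowing curvature.

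A reader might infer that the cut endangers the primary result, because a qualifying covariate turns the adjusted model into the primary one. The documents do not support that: both criteria must be met, which is rare under randomization, and the form of age then matters little for the treatment effect. A reader might also infer that the older group will be too small to use. That depends on an age mix that the documents do not give.

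**Conclusion.** The point holds as a minor one. Age is cut at 50 without a stated reason, and the cut weakens the exploratory age analyses if age acts gradually. The loss of about 11 to 33 points at n = 60 rests on a linear relation with partial r about 0.33, age mixes with roughly 17% to 50% of donors aged 50 or over, and alpha of 0.05 or 0.10. With weaker relations the loss shrinks, but power is then low in either form. The primary treatment comparison is practically unaffected: age enters the adjusted model in under about 9% of trials at this strength, and the gain from the continuous form is then about 1 to 2 points.

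**What to change.** In section 11.1, replace the two-level age entry with age in years as a continuous variable, for both the age-by-treatment analysis and any adjusted model. Specify a linear term with a check for curvature, such as a quadratic or restricted cubic spline term. Keep the under-50 and 50-or-over groups for descriptive display of the iron effect only. If there is a substantive reason for 50, one sentence giving it would also settle the point.

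The cost is a short wording change. Age has to be known to confirm eligibility, so no new data, visits or subjects are needed. The downside is the lower power under a true step at 50. A curvature term also uses a degree of freedom or more, which matters somewhat with 52 to 60 subjects.

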1. Iron therapy will improve neurocognition and emotional well-being in donors with iron deficient erythropoiesis.
2. Metabolite levels in the transfusate will be associated with 24-hour post-transfusion RBC recovery and iron status.

Study Schema:

This is a randomized, controlled, double-blind clinical trial. 60 healthy regular donors who meet donation standards, while exhibiting iron-deficient erythropoiesis by laboratory test criteria, will donate a single standard RBC unit that will be leukoreduced and stored under standard conditions for 42 days. The FDA gold standard measure for the quality of RBCs destined for transfusion is the 51Cr-radiolabeled 24-hour RBC recovery study. Thus, a small aliquot of the transfused RBCs will be radiolabeled and injected into the volunteers on day 41 or 42 of storage. RBC recovery will be calculated from samples obtained at 5min, 7.5min, 10min, 12.5min, 15min, 30-minutes, 1-hour and 24 hours after autologous infusion as per the standardized protocol.⁴ For secondary outcomes, study surveys and neurocognitive assessments to assess symptoms of anemia and iron deficiency will also be performed prior to donation and prior to infusion.

In a prospective, randomized, double-blind manner, these donors will then receive either intravenous saline or low-molecular weight iron dextran (or ferric carboxymaltose if iron dextran is unavailable due to supply) within 1-day to 4-weeks after the first post-transfusion recovery study. After five months, they will donate a second RBC unit, similarly stored for 42 days, and autologous 51-chromium 24-hour post-transfusion RBC recoveries will again be determined. The primary outcome will be the group mean difference in 24-hour post-transfusion recovery difference from after treatment to baseline, between the groups receiving intravenous saline and iron.

[figure not shown]

TABLE OF CONTENTS

1. Background and Significance.....	7
2. Objectives	
2.1. Primary Hypothesis.....	11
2.2. Secondary Hypothesis.....	11
3. Study Population	
3.1. Enrollment Inclusion criteria.....	11
3.2. Enrollment Exclusion criteria.....	12
4. Trial Enrollment	
4.1. Screening / Recruitment.....	12
4.2. Randomization.....	13
4.3. Blinding.....	14
5. Interventions	
5.1. Blood donation.....	15
5.2. Chromium-51 post-transfusion RBC recovery	15
5.3. Total Dose Iron Infusion.....	16
5.4. Cognitive and Emotional Status Assessment.....	18
5.4.1. Cognition.....	18
5.4.2. Emotion.....	20
5.4.3. Hearing.....	20

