4.2 Randomization

Randomization will be performed using a computerized system with equal allocation (1:1) to iron repletion or placebo. Randomization will be stratified by gender; randomly permuted block sizes of 4, 6, or 8 will be used. The moment of randomization will be recorded and will occur only after successful completion of the first post-transfusion RBC recovery study (i.e., between Day #43-71; target is the day after the post-transfusion recovery study; performed on Harkness Pavilion 10). Volunteers will be admitted to the Columbia General Clinical Research Center (GCRC) (supported by the Columbia Clinical and Translational Science Award (CTSA)). One peripheral intravenous line will be inserted and blood (2 tubes, 10mL) will be drawn for determining the 24-hour post-transfusion recovery. The subject will be randomized at this point. The randomization scheme will be created by a statistician unaffiliated with the study team and provided to the research pharmacy and DSMB prior to study initiation. The CUMC research pharmacy will be responsible for randomizing each subject to the appropriate treatment arm and will prepare either the iron treatment or saline placebo and provide it to the study team in a blinded

fashion. If a subject arrives on the day of randomization and has a fever ($T>100.4F$) or feels ill, then the 24-hour post-transfusion recovery sample will be drawn, but randomization may be held until the subject feels better and reschedules.

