10.1 Semi-Annual DSMB Reports

The DSMB will meet twice a year, either in-person or via teleconference. Reports will include:

- Baseline characteristics overall and by group
- Primary study endpoint overall and by group, (p-values to compare to early stopping boundary will only be provided after 20, 40, and 60 volunteers have been completed)
- Number, type, and severity of serious adverse events, overall and by treatment arm, with p-value for comparison of number of serious adverse events per group. This p-value will be compared to the p-value boundary from an alpha-spending approach approximating O'Brien-Fleming boundaries. No formal stopping rule is set for this comparison.
- Number, type, and severity of adverse events attributed as possibly, probably, definitely related to donation, iron or red cell infusion, overall and by treatment arm, with p-value for comparison of number of such adverse events per group. This p-value will be compared to the p-value boundary from an alpha-spending approach approximating O'Brien-Fleming boundaries. No formal stopping rule is set for this comparison.
- Proportion of subjects in each treatment arm with at least one serious adverse event possibly, probably, or definitely related to a donation, red cell or iron infusion, with p-value. This p-value will be compared to the p-value boundary from an alpha-spending approach approximating O'Brien-Fleming boundaries. No formal stopping rule is set for this comparison.
- Unexpected adverse events, and unanticipated problems overall and by treatment arm
- Site status

- Accrual
- Site/study compliance issues
- Data entry completeness and data QA

11. Statistical Considerations

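### Fix one primary model, treatment plus gender: section 11.1 leaves the test open, appears to let a data-dependent screen choose the model, and never includes the stratification factor by default

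*Combined protocol and SAP*

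**What the plan says.** The synopsis (Study Schema) defines the target: "The primary outcome will be the group mean difference in 24-hour post-transfusion recovery difference from after treatment to baseline", compared between the iron and saline arms.

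Section 4.2 (Randomization) gives the design: "Randomization will be stratified by gender; randomly permuted block sizes of 4, 6, or 8 will be used". Gender is the only stratification factor.

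The first paragraph of section 11.1 (Analysis Plan) tests the primary null hypothesis by intention to treat, "using a t-test, or nonparametric equivalent, of the between-group difference in means of the within-subject change" in recovery. It gives neither a default nor a criterion for leaving the t-test.

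The second paragraph opens with a secondary regression on zinc protoporphyrin. It then examines gender, race and age "to see if we can identify one or more that may be effect modifiers". The rule that follows reads "The specific criteria for inclusion are: (i) difference by treatment group significant at" a two-sided 0.10 level, and (ii) a relation to outcome at the same level. If any covariate qualifies, "they will be incorporated in an adjusted model, and that model will become the primary analysis". "Otherwise, the simple model will be primary".

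For the group sequential boundary, section 10.1 says "p-values to compare to early stopping boundary will only be provided after 20, 40, and 60 volunteers have been completed". Section 11.3 compares a Z-score with Table 3 (3.7103, 2.5114, 1.9930). Neither section names the test or model behind the statistic.

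**The concern.** Three features of section 11.1 combine.

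- **Open test.** A rank test does not estimate the difference in means that the synopsis names as the primary outcome, so the choice between the two tests should not be left open.
- **Data-dependent model.** Criterion (i) uses treatment arm and criterion (ii) uses outcome. On the plainest reading, the primary model is therefore not known until unblinded data have been examined, and nothing says whether the screen is rerun at 20 and 40 completers.
- **Stratification factor left out.** Criterion (i) is undefined. If it means baseline imbalance, stratified blocks practically prevent gender from ever meeting it. If it means interaction, which the stated search for effect modifiers may suggest, the wording does not say so. On either reading gender is not in the model by default.

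At stake is efficiency and a single named statistic. When randomization balances a prognostic factor and the analysis ignores it, the standard error is too large and the test is conservative.

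**Working it through.** **Inputs from the documents.** SD 5, target difference 4 points, two-sided alpha 0.05, 26 evaluable per arm, 60 randomized with up to 15% dropout (section 11.2); stratified blocks of 4, 6 or 8 (section 4.2); Table 3 boundaries (section 11.3).

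**Assumptions not in the documents.** 60% female; 30% not white; 50% aged 50 or over; race and age without effect; gender shifts the change by 0, 2 or 4 points; 52 analysed.

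**1. The plan's own figure.** The noncentrality is 4 / (5 × √(2/26)) = 2.884. With 50 degrees of freedom the t-test has power 80.7%, so 26 per arm reproduces, with SD 5 taken as the SD of the analysed change. Adding gender leaves 49 degrees of freedom and power 80.7%, so the adjustment costs nothing visible when gender is irrelevant.

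**2. Closed form, 4-point gender shift, total SD held at 5.** The residual SD is √(25 − 0.6 × 0.4 × 4²) = √21.16 = 4.6. With gender balanced between arms, the treatment difference varies with SD 4.6, while the t-test uses 5. Its critical value of 2.009 therefore acts as 2.009 × 5/4.6 = 2.183.

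- Size of the t-test: P(|t₅₀| > 2.183) ≈ 3.4%.
- Noncentrality: 4 / (4.6 × √(2/26)) = 3.135. Power is about 82.7% for the t-test (critical value 2.183) and 86.7% for treatment plus gender (critical value 2.010, 49 df).

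**3. Simulation with stratified blocks and random dropout** (40,000 trials per cell; Monte Carlo SE about 0.1 points for size, 0.2 for power; total SD 5; selected covariates entered as main effects). Cells show size / power in %.

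| Gender shift | Rule, (i) = imbalance | Rule, (i) = interaction | t-test | Treatment + gender |
|---|---|---|---|---|
| 0 | 4.8 / 80.1 | 4.9 / 80.5 | 4.9 / 80.5 | 4.9 / 80.4 |
| 2 | 4.5 / 80.4 | 4.6 / 80.9 | 4.5 / 80.9 | 4.9 / 81.9 |
| 4 | 3.5 / 81.6 | 3.7 / 82.4 | 3.6 / 82.2 | 4.9 / 86.4 |

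The simulation agrees closely with step 2. Over 50% to 75% female, the gain of the gender model over the imbalance rule is 0.3–0.4 power points with no shift, 1.0–1.7 at 2 points and 4.0–5.2 at 4 points.

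If gender variance instead lies on top of SD 5 (total √(25 + 3.84) = 5.37), power at a 4-point shift is 75.6 / 76.5 / 76.1 / 80.6% in the same column order.

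**4. Can gender enter under the rule?** Read as imbalance, criterion (i) is met by gender in 0% of trials at 50% female, 0.015% at 60% and 0.08% at 75%. Read as interaction, gender meets both criteria in about 1% (no shift), 3–4% (2 points) and 7–9% (4 points).

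**5. Looks at 20, 40 and 60 against Table 3** (total SD 5, imbalance reading; gender shift 0 / 2 / 4). Overall size is 5.0 / 4.6 / 3.4% for the t-test, 4.9 / 4.6 / 3.4% for the rule rerun at each look, and 5.0 / 5.1 / 5.0% for treatment plus gender. If rerun, the rule selects different models across looks in 5.2% of null trials and 8.5% with a 4-point treatment effect. It falls on the other side of the boundary from the t-test in about 0.8% of trials at 40 completers and under 0.1% at 20.

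**6. Open test choice** (normal data, 26 per arm, 100,000 trials). The t-test and the rank-sum test disagree at 0.05 in 2.0% of null trials and 5.3% with a 4-point effect. Always taking the significant one would give 5.9% size, an upper bound and not a prediction.

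**The case against.** The strongest defence is textual. The first paragraph of section 11.1 already states the primary test, and the rule comes in the next paragraph, which is about a secondary regression. The only model mentioned before the rule is that regression, so the terms simple and primary may belong to it alone. This stands as a possible reading. It would remove the switching problem, but not the open test or the absence of gender.

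Second, the gender model could be called a preference. The endpoint is a within-subject change, so a stable gender difference in recovery cancels. A 4-point gender shift is as large as the whole target effect, and other fixed models, such as one with baseline recovery, are defensible. This stands as a limit on the size of the gain. It does not justify leaving the model open, and gender is the factor the design already balances.

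Third, the ordinary reading of sections 10.1 and 11.3 is that the same test applies at every look. That is fair: the interim silence alone would be only a missing detail.

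A reader might infer that the switching rule inflates type I error. The simulations do not show this when selected covariates enter as main effects, and the covariates and thresholds are pre-specified. That result is limited, because race and age were set to have no effect. In a second set of simulated trials with all three covariates prognostic, also with main-effect entry, the rule was more conservative (overall size 3.9% at 3-point and 2.7% at 5-point effects). If a selected interaction were entered with reference coding, size was 5.6% against 5.0% for the t-test; with centred coding it was 5.0%. The documents specify neither form. Bias was not reported, so no claim is made about it.

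**Conclusion.** The point holds as a free improvement. Section 11.1 leaves the primary test open, and on its plainest reading a screen on arm and outcome decides the primary model. On every reading the only stratification factor is absent by default; if criterion (i) means imbalance, it is practically barred.

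The size is modest and conditional. At an assumed 4-point gender shift with total SD 5, about 4 power points are forgone (82% against 86%) and size drops to about 3.5%. At 2 points, about 1 point of power is forgone. With no shift, nothing material changes either way. The documents do not say whether gender predicts the change.

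A reader might also infer that the trial is underpowered because of this. That is not supported: planned power of about 80% is kept if the stated SD of 5 is the total SD. The fall to about 76% needs both a 4-point shift and gender variance outside that SD, and section 11.2 indicates neither.

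**What to change.** State which analysis the word primary refers to in the second paragraph of section 11.1, delete the switching rule, and name one primary analysis. Suggested text:

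*Change in 24-hour recovery (PTR2 minus PTR1) is analysed in a linear model with treatment and gender as fixed terms. The same model is used at the 20- and 40-completer looks and at the final analysis, whatever number complete. The two-sided p-value of the treatment coefficient is converted to Z, with the sign of the coefficient, for the group sequential boundary. Gender is omitted only if all analysed subjects at a look are of one gender.*

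The treatment coefficient estimates the group mean difference that the synopsis names. The final analysis is not tied to 60 completers because section 11.2 randomizes 60 and allows up to 15% dropout.

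Make the rank-based test and a model adding race and age sensitivity analyses. Label treatment-by-gender, treatment-by-race and treatment-by-age interactions exploratory.

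Cost: one degree of freedom and SAP wording, with no extra subjects and no new data.
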